### 5.3.2. Examination of Subgroups

No subgroup analysis is planned in this study.

### 5.4. Multiple Comparisons and Multiplicity

There is a single primary endpoint. There are no adjustments for multiplicity across the secondary endpoints.

### 5.5. Other Considerations for Data Analyses and Data Handling Conventions

Other considerations for data analyses and data handling conventions are outlined in the appendices:

Section	Component
10.3	Appendix 3: Assessment Windows
10.4	Appendix 4: Study Phases and Treatment Emergent Adverse Events
10.5	Appendix 5: Data Display Standards & Handling Conventions
10.6	Appendix 6: Derived and Transformed Data
10.7	Appendix 7: Reporting Standards for Missing Data
10.8	Appendix 8: Values of Potential Clinical Importance

## **6. STUDY POPULATION ANALYSES**

### **6.1. Overview of Planned Study Population Analyses**

The study population analyses will be based on the ITT population, unless specified to be on ASE population.

Study population analyses including analyses of subject's disposition, protocol deviations, demographic and baseline characteristics, prior and concomitant medications, and exposure and treatment compliance will be based on GSK Core Data Standards. Details of the planned displays are presented in [Appendix 10: List of Data Displays](#).

### **6.2. Disposition**

The study population summary will use the ASE population and show the number of subjects overall who were enrolled, the number of screen failures and the number with each reason for screen failure. It will also show the number of subjects who were randomised and who were in the ITT population.

For the ITT population reasons for withdrawal summary will show the number and percentage of subjects who completed the study, who withdrew prematurely from the study and who reported each primary and sub-reason for withdrawal.

### **6.3. Medical Conditions**

The number and percentage of subjects reporting each current medical condition will be presented. This table will include a subheading of 'Cardiovascular Risk Factors,' which will summarise the information taken from the cardiac disorders page in the eCRF. All medical conditions must be summarised on this table regardless of frequency. This will be repeated for past medical conditions.

### **6.4. Concomitant Medications**

Non-COPD medications will be summarised by Anatomical-Therapeutic-Chemical (ATC) level 1 and ingredient. COPD medications will be summarised by Respiratory Medication Class (RMC), and will be derived for each COPD concomitant medication. Multi-ingredient medications will be presented according to their combination ATC classification rather than the classifications of the ingredients.

COPD and non-COPD medications will be listed separately. A listing of the relationship between ATC Level 1, ingredient and verbatim text will be produced for non-COPD medications only.

## 7. EFFICACY ANALYSES

### 7.1. Primary Efficacy Analyses

#### 7.1.1. Endpoint

Percentage of participants with zero errors after 28 days of use

#### 7.1.2. Summary Measure

Odds Ratio: The odds of having zero errors on ELLIPTA after 28 days used compared to the odds of having zero errors on DISKUS + HandiHaler after 28 days use.

#### 7.1.3. Population of Interest

The primary efficacy analyses will be based on the Intent-To-Treat population, unless otherwise specified.

#### 7.1.4. Strategy for Intercurrent (Post-Randomization) Events

There are three intercurrent events identified which could impact upon the estimand of interest:

- The subject could withdraw from randomised study device sequence and therefore withdraw from the study
- The subject could change their standard COPD maintenance medication device to one delivered via ELLIPTA, DISKUS or HANDIHALER; these subjects should have been withdrawn from the study according to the protocol.
- The subject could attend the visit without the device/s they were randomised to, in which case correct use cannot be assessed as described in the protocol.

Rescue Medication use and change to maintenance COPD medication which is not delivered via ELLIPTA, DISKUS or HANDIHALER are not considered intercurrent events.

Subjects who withdrew in period 2 complete an error assessment at the early withdrawal visit, however no error assessments were made if they withdrew in period 1

Two estimands will be assessed:

- **Primary Estimand:** The treatment effect to be estimated is the principle strata of all subjects who stayed on their randomised study device sequence and did not change their standard COPD maintenance medication device to one delivered via ELLIPTA, DISKUS or HANDIHALER, throughout both 28 day treatment periods. In this analysis subjects with intercurrent events will have their data set to missing from the point of that event and so are not included in this analysis. Data from the early withdrawal visit will not be used.
- **Supplementary Estimand:** The treatment effect to be estimated will be the composite effect of initial randomized treatment. Error assessment from the early

withdrawal visit will be used for those who withdrew prematurely from the study in period 2. For those who withdrew without providing an assessment in period 2 it will be assumed that they made an error.

If subjects experience an intercurrent event in Period 1 then they should not have entered Period 2 and so their data in Period 2 will be set to missing for all estimands.

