6. A health care professional trained on the inhalers will conduct the assessments of the participant's ability to correctly use the returned inhaler (s) at Visits 2 and 3 following return of the inhaler (s) used for the previous dosing period. This should be completed at Early Withdrawal Visit if a participant has taken one or more doses of the inhaler at home.
7. Participants will record medical problems and medications taken on the Medical Problems/Medications Taken Worksheet between visits.
8. Safety assessments will be completed at the Early Withdrawal Visit: however, inhaler preference questionnaires will not be completed.

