10.2. Sample Size Determination

The sample size calculations for this study have been based on the primary endpoint, which is the percentage of participants making zero errors in each treatment group (ELLIPTA or DISKUS + HandiHaler) after 28 days use.

The estimates of inhaler errors were taken from the overall errors reported in the 200301 study for each individual inhaler (ELLIPTA, DISKUS and HandiHaler) separately. Although this study is only assessing combined errors in the DISKUS + HandiHaler treatment group, individual inhaler errors were used to estimate the combined error rate in order to provide a conservative estimate. By doing this it assumes that participants, who made no errors on the DISKUS inhaler, would not make any errors of the HandiHaler inhaler and vice-versa.

As the 200301 study only had a single visit, no estimates were available for error rates over 28 days, however the study did provided estimates of participant errors after reading the PIL and after being instructed on correct use by a HCP up to three times. As participants will have the PIL for 28 days, and can be instructed by a HCP at the inhaler dispensing visit if necessary, both estimates of error rates along with a sensitivity analysis examining some of the potential error rates between were used to inform sample size calculations.

Using 10,000 simulations, a total of 216 participant (54 per treatment sequence) provide at least 90% power to show a statistically significance difference between the overall error rate of the ELLIPTA inhaler versus DISKUS + HandiHaler inhalers, for all of the paired treatment error rates shown in [Table 1](#).

Table 1 Error rates of ELLIPTA vs. DISKUS + HandiHaler achievable with 90% power, 5 % Type 1 error using a total of 216 participants

ELLIPTA Error Rate	DISKUS + HandiHaler Error Rate
33%	>=50%
30%	>=47%
20%	>=35%
10%	>=23%
5%	>=15%

Conditional logistic regression and a two-sided 5% significance level were used as the analysis method for all simulations performed. As it is expected that some participants would drop out or change inhalers during the study, with 10% withdrawal it would be

necessary to enrol 240 participants (60 per treatment sequence) to ensure there were 216 participants with evaluable data at the end of the study.

For the purpose of this study an evaluable participant is defined as a randomized participant who completed error assessments for both randomized treatment groups.

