**7.1.5.1. Statistical Methodology Specification**

Endpoint

 
Percentage of participants with zero errors after 28 days of use
 

Model Specification

 
The primary endpoint of the percentage of participants with zero errors after 28 days of use, will be analysed using the Intent-to-treat population.
 
This endpoint will be analysed using conditional logistic regression with subject as fixed strata, and treatment option and period as fixed effects.
 
If there are low cell counts (<5) in the cross tabulation of subjects making errors on ELLITPA compared to DISKUS + HandiHaler or the model fails to converge with all cell counts >=5, then the exact conditional logistic regression with subject as fixed strata, and treatment option and period as fixed effects will be used instead.
 

Model Checking & Diagnostics

 
None
 

Model Results Presentation

 
The odds ratio, 95% CI and p-value will be presented for the comparison between treatment options. It will be based on a two-sided hypothesis testing approach of superiority.
 

Sensitivity and Supportive Analyses

 
A sensitivity analysis will be performed using the Cochran-Mantel-Haenszel (CMH) test. The CMH test serves as a stratified approximation to the Mainland-Gart test, a variation of a one-sample chi-square test that accounts for study inhaler sequence (period). A subject who had an error with both devices or who had no errors with both devices does not provide any information about the superiority of either device. Only those subjects who had error(s) in one device and had no error in the other device are counted for in the Mainland-Gart test.
 
For the supplementary estimand a tipping point analysis will be performed to assess how robust the composite estimand is to missing data assumptions. To assess this the outcomes for subjects with missing error assessment in period 2 will be varied in the two treatment groups independently from imputing 0 subjects with an error to all subjects with an error.
 

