**10.10.5. Efficacy Tables**

Overall Summary of Errors					
No.	Population	IDSL / TST ID / Example Shell	Title	Programming Notes	Deliverable
2.01	ITT	EFF_T01	Summary of Errors on ELLIPTA		SAC
2.02	ITT	EFF_T01	Summary of Errors on DISKUS + HandiHaler	Page by DISKUS + HandiHaler Errors, DISKUS Errors and HandiHaler Errors	SAC
2.03	ITT	EFF_T06	Summary of Overall Errors		SAC
2.04	ITT	EFF_T06	Summary of Overall Errors by Age	Use age categories: 40-64, 65-74 and $\geq 75$ .	SAC
2.05	ITT	EFF_T06	Summary of Critical Errors		SAC
Primary Efficacy Tables					
Percentage of Overall Errors					
2.06	ITT	EFF_T04	Analysis of Percentage of Participants making Zero Errors after 28 days use (Primary Estimand: Principle Strata)		SAC
2.07	ITT	EFF_T04	Analysis of Percentage of Participants making Zero Errors after 28 days use (Supplementary Estimand: Composite)		SAC
2.08	ITT	EFF_T09	Tipping Point Analysis of Participants making Zero Errors after 28 days use (Supplementary Estimand: Composite)		SAC
2.09	ITT	EFF_T07	Sensitivity Analysis of Percentage of Participants making Zero Errors after 28 days use (Primary Estimand: Principle Strata)		SAC

Overall Summary of Errors					
No.	Population	IDSL / TST ID / Example Shell	Title	Programming Notes	Deliverable
2.10	ITT	EFF_T07	Sensitivity Analysis of Percentage of Participants making Zero Errors after 28 days use (Supplementary Estimand: Composite)		SAC
Secondary Efficacy Tables					
Percentage of Critical Errors					
2.11	ITT	EFF_T04	Analysis of Percentage of Participants making Zero Critical Errors after 28 days use (Primary Estimand: Principle Strata)		SAC
Number of Overall Errors					
2.12	ITT	EFF_T01	Summary of Number of Errors by Type for each Inhaler after 28 Days of Use	Replace 'Early withdrawal' column with 'Difference (ELLIPTA minus DISKUS + HandiHaler)	SAC
2.13	ITT	EFF_T08	Summary of Number and Change in Errors per Participant for each Treatment Group (V2 and V3) after 28 Days of Use		SAC
2.14	ITT	EFF_T08	Summary of Number and Change in Errors for each Treatment Group in Participants with One or more Errors after 28 Days of Use		SAC
Exploratory Efficacy Tables					
Preference Attributes					
2.15	ITT	EFF_T04	Analysis of Percentage of Participants with Zero Errors after 28 Days of Use, including the Number of Prescribed Maintenance Inhalers as a Covariate.		SAC

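### The supplementary 'composite' estimand is a hybrid: a Period 2 withdrawal counts as an error only when there is no Early Withdrawal assessment

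*SAP*

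**What the plan says.** SAP 7.1.4 lists withdrawal from the randomised device sequence as an intercurrent event. The primary estimand leaves withdrawals out and does not use Early Withdrawal data. Of the supplementary estimand it says: "The treatment effect to be estimated will be the composite effect of initial randomized treatment". Two scoring rules follow:

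- **Assessed withdrawals.** The error assessment from the early "withdrawal visit will be used for those who withdrew prematurely from the study in period 2".
- **Unassessed withdrawals.** A Period 2 withdrawal who gives no assessment is assumed to have made an error.

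The same section states, without a percentage, that Period 2 withdrawals do undergo an error assessment at the Early Withdrawal visit. Protocol 8.2 tells sites to try hard to arrange that visit. On the demonstration itself, footnote 6 of the protocol's Schedule of Activities says: "This should be completed at Early Withdrawal Visit if a participant has taken one or more doses of the inhaler at home". Participants with an intercurrent event in Period 1 have Period 2 set to missing under every estimand.

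SAP 7.1.5.1 adds: "For the supplementary estimand a tipping point analysis will be performed to assess how robust the composite estimand is to missing data assumptions". The outcomes varied there are the missing Period 2 assessments. Table 2.07 in SAP 10.10.5 is titled "Analysis of Percentage of Participants making Zero Errors after 28 days use (Supplementary Estimand: Composite" (final bracket dropped here). Tables 2.08 and 2.10 carry the same estimand label.

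**The concern.** Under a composite strategy the intercurrent event is part of the outcome: leaving the device is itself a failure. Here that is true only of withdrawals who skip the last visit. Someone who leaves soon after training, having taken one home dose, and then demonstrates correctly enters Table 2.07 as having made no errors after 28 days of use.

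Table 2.07 is the main check on a primary analysis that omits withdrawals. If nearly all Period 2 withdrawals are assessed, no planned efficacy model counts a withdrawal as a failure: the primary model excludes them, the supplementary model scores them on the demonstration, and Period 1 withdrawals are missing throughout. The tipping point does not close the gap, because it never alters the outcome of an assessed withdrawal. A reader of the report could take agreement between Tables 2.06 and 2.07 as evidence that device-related dropout does not matter, when the rule had little chance of showing otherwise.

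**Working it through.** **1. The plan's own figures.** Protocol 10.2 states: "Using 10,000 simulations, a total of 216 participant (54 per treatment sequence) provide at least 90% power", and on method: "Conditional logistic regression and a two-sided 5% significance level were used as the analysis method for all simulations performed". Allowing for 10% withdrawal, 216 / 0.90 = 240. Simulating 108 per device order with independent responses gives power of 94.6, 95.2, 94.0, 95.4 and 93.6% for the five Table 1 pairs, in agreement with the stated 90% or more.

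**2. Inputs.** From the documents: 240 randomised, so 120 per device order, and the Table 1 error rates. Assumed, because the documents are silent: 12 Period 2 withdrawals and none in Period 1, their split by device, attendance at the Early Withdrawal visit, errors at completers' rates there, and independence within participant.

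**3. Formula.** Only discordant participants inform the conditional model. In each order let *b* be the expected number with an error on ELLIPTA only, and *c* the number with an error on DISKUS + HandiHaler only. Adjusted for period,

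OR = exp{[ln(c1/b1) + ln(c2/b2)] / 2} = √[(c1/b1)(c2/b2)].

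At 5% versus 15%, the per-participant probabilities are 0.05 × 0.85 = 0.0425 for *b* and 0.15 × 0.95 = 0.1425 for *c*. Let uE and uD be the withdrawals scored as errors by rule on ELLIPTA and on DISKUS + HandiHaler:

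- ELLIPTA second: b = 0.0425(120 − uE) + 0.85uE; c = 0.1425(120 − uE)
- ELLIPTA first: b = 0.0425(120 − uD); c = 0.1425(120 − uD) + 0.95uD

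**4. Results at 5% versus 15%** (splits are ELLIPTA/DISKUS + HandiHaler)

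| Rule | uE / uD | ELLIPTA second: b, c | ELLIPTA first: b, c | OR |
|---|---|---|---|---|
| SAP rule, full attendance, any split | 0 / 0 | 5.10, 17.10 | 5.10, 17.10 | 3.35 |
| SAP rule, 10/2, 75% attend | 2.5 / 0.5 | 7.12, 16.74 | 5.08, 17.50 | 2.85 |
| SAP rule, 10/2, 50% attend | 5 / 1 | 9.14, 16.39 | 5.06, 17.91 | 2.52 |
| Every withdrawal an error, 10/2 | 10 / 2 | 13.18, 15.68 | 5.02, 18.72 | 2.11 |
| Every withdrawal an error, 6/6 | 6 / 6 | 9.95, 16.25 | 4.85, 21.95 | 2.72 |
| Every withdrawal an error, 2/10 | 2 / 10 | 6.72, 16.82 | 4.68, 25.18 | 3.67 |

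Complete pairs, as in the primary analysis, give 0.1425 / 0.0425 = 3.35.

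**5. Where the gap is small.** At 33% versus 50%, b = 0.33 × 0.50 = 0.165 and c = 0.50 × 0.67 = 0.335, so the SAP rule at full attendance gives 2.03. With 6/6 and every withdrawal an error, ELLIPTA second has b = 18.81 + 3.00 = 21.81 and c = 38.19; ELLIPTA first has b = 18.81 and c = 38.19 + 4.02 = 42.21. Then OR = √(1.751 × 2.244) = 1.98.

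**6. Cross-check under a different pattern.** 240 randomised, 10% withdrawing while on ELLIPTA and none on the other regimen (about 12 withdrawals in each period), 2,000 simulated trials per setting, 5% versus 15%. With all Period 2 withdrawals assessed, the supplementary OR is 3.45 against 3.46 for the primary. With half assessed it is 2.42 against 3.53. With every Period 2 withdrawal an error it is 1.91.

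**The case against.** The strongest reply is that the rule responds to withdrawal more than the label problem suggests. A reader might infer that withdrawal is no failure component at all, or that Table 2.07 must repeat the primary result whichever device drives dropout. The documents support neither. Unassessed Period 2 withdrawals are errors, and the 75% and 50% rows above show the odds ratio moving well away from 3.35. Assessed withdrawals are scored on what they actually do. If the 10 ELLIPTA withdrawals erred at 50%, ELLIPTA second would have b = 4.675 + 10 × 0.5 × 0.85 = 8.925 and c = 15.675 + 10 × 0.15 × 0.5 = 16.425. That gives an OR of √(1.840 × 3.353) = 2.48 even at full attendance. This part of the reply stands, so the concern must be stated conditionally.

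It is also fair that the 10/2 split is invented. With 6/6 the simulated chance of p < 0.05 hardly differs between the SAP rule and all-as-error: about 96% against 94% at 5% versus 15%, and 97% against 96% at 33% versus 50%.

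Nor is scoring every withdrawal as an error plainly better. Protocol 8.2 includes reasons such as withdrawn consent, pregnancy and study closure, which need not concern the device. In the 10/2 case, imposed errors supply 8.5 of the 13.2 ELLIPTA-only discordant pairs in one order, so that odds ratio largely measures dropout. This argues against replacing the existing analysis, but not against naming it correctly.

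Finally, the tipping point is consistent with the rule actually written, and shell EFF_T01 already has an Early Withdrawal column. Both are true, but neither shows the effect of treating assessed withdrawals as failures.

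**Conclusion.** The point holds in a limited form. For assessed Period 2 withdrawals, withdrawal is not a failure under SAP 7.1.4, so Tables 2.07, 2.08 and 2.10 carry a label that their rule does not deliver. Table 2.07 nearly repeats the primary odds ratio under unequal withdrawal only if attendance is near complete and withdrawals err at completers' rates. The SAP presumes the first; neither document gives evidence on the second.

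The size depends on the assumptions. At 5% versus 15% with 12 Period 2 withdrawals and full attendance, the SAP rule gives 3.35 against 2.11 (10/2), 2.72 (6/6) or 3.67 (2/10) for a composite over Period 2. With 10/2 the chance of p < 0.05 falls from about 96% to about 70–72% (two simulation runs). At higher error rates with balanced withdrawal the difference is negligible.

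A reader might also infer that the primary result is compromised. It is not: the primary analysis does not use this rule. The issue is how far a supplementary table can reassure.

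**What to change.** In SAP 7.1.4 and in Tables 2.07, 2.08 and 2.10, retitle the existing analysis *last available assessment, Period 2 withdrawals without assessment imputed as error*. Keep its model and its tipping point as they are.

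Add one row to Table 2.07 that scores every Period 2 withdrawal as having at least one error on the Period 2 regimen, whatever the Early Withdrawal demonstration showed. Label it as the composite for Period 2 withdrawals, and note that Period 1 withdrawals remain missing under all estimands, so it is not a composite over the whole study.

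The cost is SAP wording, one derivation flag and one extra row, with no new data. The added row may be less favourable and will partly reflect withdrawals unrelated to the device, which a footnote should say. The change should be made before database freeze.

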8.2. Withdrawal/Stopping Criteria

Any participant may voluntarily discontinue participation in this study at any time. Further, an investigator may, at their discretion, discontinue any participant from participating in the study at any time. All investigators with discontinued participants from their sites will be required to make every effort to schedule those participants for an Early Withdrawal Visit as soon as possible. Accordingly, the reasons for each participant's withdrawal must be recorded in the case report form (CRF) and may include the following: AE, consent withdrawn, lost to follow-up, protocol deviation, study closed/terminated, COPD exacerbation, and investigator's discretion. Specific regards should be given to distinguish withdrawals due to an AE, COPD exacerbation, and protocol deviation. The occurrence of serious adverse event (SAE) that results in withdrawal will be recorded as withdraw due to "adverse event".

A participant will also be withdrawn from the study if they experience any of the following:

- COPD exacerbation which requires hospitalization.

- COPD exacerbation which requires emergency treatment, which would in the investigator's judgement pose continued participation in this study as an unacceptable risk (i.e. unable to demonstrate correct use).
- AE/SAE that would, in the investigator's judgement, make continued participation in the study an unacceptable risk.
- Use of any medication delivered by the ELLIPTA, DISKUS or HandiHaler inhalers (excluding placebo inhalers).
- Participant reports becoming pregnant during the study.

If a participant is prematurely discontinued from the study, the investigator must make every effort to perform the assessments as specified in the SoA at an early withdrawal (EW) visit as soon as possible and then discontinue the participant from the study.

Safety assessments will be completed at the Early Withdrawal Visit; however, inhaler preference questionnaires will not be completed. After completion of the Early Withdrawal Visit, participants will be discharged from the study.

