**7.3.4. Strategy for Intercurrent (Post-Randomization) Events**

As these are exploratory endpoints only the primary estimand will be assessed.

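### SAP 7.1.4 handles a device forgotten at Visit 2 as if the participant should have left the study, and so discards observed Period 2 data from exploratory and descriptive analyses

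*SAP*

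**What the plan says.** SAP 7.1.4 lists three intercurrent events: withdrawal, a change of maintenance device to ELLIPTA, DISKUS or HandiHaler, and a third, "The subject could attend the visit without the device/s they were randomised to". Two handling rules follow. Under the primary estimand, data are missing from the point of the event. Separately, for all estimands, "If subjects experience an intercurrent event in Period 1 then they should not have entered Period 2", and Period 2 data are set to missing. Neither rule singles out any of the three events.

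The principal stratum in the same section is narrower. It consists of participants who stayed on their device sequence and did not switch to one of the three study-type devices. Bringing the device to the visit is not part of the definition.

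SAP 7.2.4 applies the primary estimand to the secondary endpoints. SAP 7.3.4 does so for the exploratory ones: "As these are exploratory endpoints only the primary estimand will be assessed". SAP 10.7.2.2 refers missing correct-use and questionnaire data back to the estimand. It has one exception: if only one of DISKUS and HandiHaler was assessed and an error was seen on it, the combined assessment counts as an error.

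Protocol 8.2 introduces its list with "A participant will also be withdrawn from the study if they experience any of the following". The list covers two kinds of COPD exacerbation, an AE or SAE making participation an unacceptable risk, use of medication from a study-type inhaler, and pregnancy. Arriving without the study inhaler is not on it.

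**The concern.** The Period 1 inhaler is returned at Visit 2, so in Period 1 the third event can only happen at Visit 2. Unless there is another reason to withdraw, that participant is given the second regimen, uses it for 28 days and attends Visit 3. The only result that cannot be obtained is the Day 28 check on the first regimen.

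The rule removes much more than that. It removes the Visit 2 leaflet check on the newly dispensed inhaler, the Period 2 Day 28 check and error counts, and the Visit 3 preference answers. None of these needs the forgotten device. At stake are observed data for four exploratory endpoints (the leaflet-stage comparison and three preference questions) and for the descriptive secondary summaries. A deletion rule would also be resting on a premise that the protocol does not support.

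**Working it through.** **Step 1: does the premise fit each event?**

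| Event in Period 1 | Should the participant have stopped before Period 2? | Outside the SAP's stratum? |
|---|---|---|
| Withdrawal | Yes, by definition | Yes |
| Switch to a study-type device | Yes, Protocol 8.2 | Yes |
| Visit 2 without the device(s) | No criterion in Protocol 8.2 | No |

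**Step 2: what is deleted after the third event?**

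| Data | When obtained | Needs the forgotten device? | Under SAP 7.1.4 |
|---|---|---|---|
| Leaflet check, first regimen | Visit 1 | No | Kept |
| Day 28 check, first regimen | Visit 2 | Yes | Missing anyway |
| Leaflet check, second regimen | Visit 2, on the new inhaler (Protocol 9.1.1) | No | Deleted |
| Day 28 check, error count and change, second regimen | Visit 3 | No | Deleted |
| Preference answers | Visit 3 (Protocol 9.1.4) | No | Deleted |

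The leaflet pair (rows 1 and 3) is complete in the database but loses its second member. The change summary in the SAP mock shells is Day 28 minus the leaflet assessment within each treatment; for Period 2 both values are observed and both go.

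**Step 3: effect on the conditional models.** With participant as stratum and treatment and period fitted, only discordant pairs contribute. Let a and b be the numbers in the ELLIPTA-first sequence with an error on ELLIPTA only and on DISKUS + HandiHaler only, and c and d the same counts in the other sequence. Then

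log odds ratio = ½[ln(b/a) + ln(d/c)], SE = ½√(1/a + 1/b + 1/c + 1/d).

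A participant with no Period 1 Day 28 result is in none of the four cells, so deleting the Period 2 result changes nothing. The possible exception is a participant starting with DISKUS + HandiHaler who brings one of the two devices and makes an error on it. SAP 10.7.2.2 gives that participant a Period 1 result (an error), while 7.1.4, if it applies, removes the Period 2 result and with it the pair. The SAP does not say whether bringing one of two devices is this event, or which section prevails.

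**Step 4: reproduce the plan's figures.** Protocol 10.2 states that "a total of 216 participant (54 per treatment sequence) provide at least 90% power" for the Table 1 error rates, and that "Conditional logistic regression and a two-sided 5% significance level were used as the analysis method for all simulations performed". I simulated 100,000 trials per pair, 108 participants per device sequence, with the two responses independent (assumption), using the Wald test from Step 3 with 0.5 added to each count when any is zero.

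| ELLIPTA / DISKUS + HandiHaler error rate | Power at 216 |
|---|---|
| 33% / 50% | 94.8% |
| 30% / 47% | 95.2% |
| 20% / 35% | 93.7% |
| 10% / 23% | 95.6% |
| 5% / 15% | 93.8% |

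All are at least 90%, and higher with positive within-participant correlation (0.1 to 0.3 tried). Enrolment: 216 / (1 − 0.10) = 240. Both stated figures reproduce.

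**Step 5: size of the leaflet-stage loss.** The share attending Visit 2 without the device is not in the documents; 1% to 10% is assumed. Pairs lost = share × 240, rounded. The plan gives no leaflet-stage power, so two Table 1 pairs are borrowed as illustration.

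| Assumed share | Pairs lost | Pairs left | Power, 33/50 (loss, points) | Power, 5/15 (loss, points) |
|---|---|---|---|---|
| 0% | 0 | 240 | 96.7% | 96.0% |
| 1% | 2 | 238 | 96.4% (0.3) | 95.8% (0.2) |
| 2% | 5 | 235 | 96.3% (0.4) | 95.5% (0.5) |
| 5% | 12 | 228 | 95.7% (0.9) | 95.0% (1.0) |
| 10% | 24 | 216 | 94.9% (1.8) | 93.8% (2.2) |

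Losses are taken from the unrounded simulation results. Starting from 216 pairs instead, the 33/50 case at 10% falls from 94.9% to 92.4% (194 pairs left). Preference answers lost are at most the same counts, since some of these participants may not reach Visit 3.

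**The case against.** The best defence is that this is loose drafting. The stated reason describes withdrawal and switching, the stratum names only those two, and 10.7.2.2 opens with assessment-level handling close to what one would want. A drafting slip is indeed the likely origin. But the third event is listed, the Period 1 sentence covers any event, and 10.7.2.2 defers to the estimand. Someone programming from the text would delete the data.

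On preference, Protocol 9.1.4 places the questionnaire after correct use has been assessed for all treatments, so one may argue that a participant with a missed assessment should not count. I read that as the order of procedures. The only written exclusion from the questionnaire is at the Early Withdrawal Visit (Protocol 8.2). The sponsor could choose to exclude these answers, but then on grounds it states, not on the ground that the participant should have left.

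It also stands that the effect is small and confined to exploratory and descriptive results, and that Period 2 results without a Period 1 partner add only to descriptive tables.

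Two stronger inferences are not supported:

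- **Uneven loss.** A reader might infer bias because one regimen has two devices to bring. The documents give no rate by device. Loss that depends on sequence alone would not bias the within-participant odds ratio with period fitted, and SAP 7.3.5.1 describes the preference test as accounting for sequence.
- **A device missing at Visit 3.** A reader might infer that this also deletes the same day's preference answers. That is one reading of the rule that data are missing from the point of the event; the text does not settle it.

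**Conclusion.** The point holds. For a device forgotten at Visit 2, SAP 7.1.4 gives a reason that Protocol 8.2 does not support and that conflicts with the SAP's own stratum, and its effect is to discard observed data unrelated to the missing assessment. Under the assumed 1% to 10%, that is 2 to 24 of 240 leaflet pairs, up to as many preference answers, and roughly 0.2 to 2.2 points of power in the leaflet-stage comparison. The power figures rest on borrowed error rates and independent responses; the true rate of the event is unknown.

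A reader might infer that the primary comparison is weakened. It is not where the Period 1 Day 28 assessment is wholly missing, and 216, 240 and the 90% power claim are unaffected by this point. The one route to losing a primary or critical-error pair is the partial DISKUS + HandiHaler assessment. This should be corrected, but it does not threaten the trial's main conclusion.

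**What to change.** In SAP 7.1.4:

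1. Restrict the sentence about not having entered Period 2, and the deletion that follows from it, to withdrawal and to a switch to ELLIPTA, DISKUS or HandiHaler.
2. For attendance without the device(s), set to missing only the Day 28 assessment that could not be done, subject to the partial-assessment exception in 10.7.2.2, and keep all other Period 1 and Period 2 data.
3. State that a device missing at Visit 3 does not remove that visit's preference answers.

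The cost is a few sentences. The model, sample size and data collection do not change. The denominators of the descriptive 28-day summaries and the missing-data counts in the tipping-point table will shift slightly, and those tables will include some participants whom the conditional model cannot use; a footnote can say so.
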